- c: The safety follow-up visit will be conducted for subjects who either terminate early from Part 1, or who complete Part 1 but do not enter Part 2. Standard follow-up visits should occur 3 and 6 months after the last dose. For subjects enrolled in Germany, France and Netherlands, follow-ups will also occur 24 months after the last dose. If there are any findings at the last post-dose follow-up, a follow-up visit will be repeated every 3 months until resolved or stabilized.
- d: The Visit 8 ECHO must be performed any time between Study Day 40 and Study Day 54. The Visit 12 ECHO must be performed any time between Study Day 90 and Study Day 113; if a subject discontinues early from the study, the ECHO should be scheduled as soon as practical. If the Study Day 43 ECHO was completed ≤ 30 days prior to early termination, the Visit 12 ECHO will not be performed provided the parent/guardian agrees to bring the subject to the clinic for the cardiac follow-up visit.
- e: Females of child-bearing potential
- f: Plasma sample for pharmacokinetic assessment will be conducted prior to the dose at Visit 8 and 1, 2, and 4-6 hours after dose administration.
- g: Plasma sample for assessment of background AED(s) will be conducted prior to the dose of AED(s) at Visits 3, 8 and 12 (Visits 6 and 10 only if clinically indicated). AED plasma sample may be collected after the morning dose of AEDs are taken, if preferable, as long as the time of last dose is accurately recorded.
- h: Study drug/diary dispensed for the Transition Period for subjects entering the open-label extension and for the Taper Period for subjects exiting the study.
- i: Site personnel will review study medication dosing procedure (titration) with parent/caregiver.
- j: Study drug administration begins in the morning of Study Day 1. Study Day 1 is considered the first day of dosing, even though subjects may receive an in-clinic dose on Study Day -1. If the first dose is taken in the clinic, it will be recorded in the eCRF, but not the subject diary; the next dose on the morning of Study Day 1 will be the first entry in the subject's diary.
- k: Only adverse events related to cardiac safety will be collected at this visit.
- 1: Visit 13 may be conducted as a phone call, provided diaries and study medication are returned by this time.
- m: An abbreviated physical and/or neurological examination to be conducted as appropriate based on last exam and reported AEs.

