6.7. VISIT WINDOWS

The following rules will be used to window data into treatment periods for by treatment period tabulations. For all by-visit tabulations, the nominal visit as recorded on the electronic Case Report Form (eCRF) will be used.

The following are the definitions for associating dates with the treatment periods of Part 1.

Baseline Period	The Baseline Treatment period will be the 28 days immediately prior to the date of the Study Day 1.
Double Blind	The Double-Blind Treatment Period start date is the date of
Treatment Period	first full daily dose (i.e. Study Day 1). The Double-Blind
Sell Call	Treatment Period end date is the last date the subject was on study treatment in Part 1.
Chy, Oblig	The Double-Blind Treatment Period consists of 16 weeks from first treatment start date, which includes 2 weeks of
S. S.	Titration period, 12 weeks of Maintenance period and 2 weeks of Taper/Transition period. The end date for efficacy
	analyses is the last day of Maintenance treatment, or Visit 12; the end date for safety analyses is the last day of

version 2.0	Syneos Health #1009529	7A
	Taper/Transition, which would be considered the date at Visit 15.	ation
	For subjects who discontinue early from the study, the double-blind treatment period end date for efficacy analyses will be the date at the early termination visit (Visit 12); the end date for safety analyses would be the date of Visit 13. If a taper is not conducted, the end date for both analyses would be Visit 12.	alithorization ereof.
Titration Period	The Titration Period begins on the first full day of treatment (Study Day 1) and extends through Visit 6 (when the subject has reached their randomization dose). The Titration Period applies to all subjects including placebo recipients. If a subject withdraws from the study prior to treatment in the maintenance period, all safety assessments and events up to and including the date of study withdrawal will be tabulated in the titration period.	ere .
Maintenance Period	The Maintenance Period covers the 12 weeks following the end of the titration period. It begins on the date of Visit 6 + 1 day and extends through the end of study/early termination visit (Visit 12).	
Titration + Maintenance Period (T+M)	The T+M period combines the Titration and Maintenance periods, beginning on the date of first treatment (Study Day 1) and extending through the end of study/end of treatment visit (Visit 12).	

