Taper/Transition Period	The Taper/Transition period consists of 2 weeks starting from end of study/early termination visit (Visit 12) + 1 day through Visit 13 (Taper) or Visit 15 (Transition to Part 2). For subjects who are not entering into the Part 2 of the study, subjects will gradually be tapered off of study medication. For subjects who are entering Part 2, subjects will enter the transition phase where all subjects will be on a dose of 0.2	
	mg/kg/day at the end of this phase.	

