A treatment-emergent adverse event (TEAE) in Part 1 is defined as any AE that based on start date information occurs after the first intake of study treatment in Part 1, but not on or after the first dose of study treatment in Part 2. For subjects who participate in Part 2, the Part 1 TEAE will include events with onset up to the day prior to the date of first dosing in Part 2. A Part 1 TEAE will be further classified into the Titration Period, Maintenance Period, and Transition/Taper Period. The Titration Period will include all events with onset from the date of the Visit 6. The Maintenance period will include all events with onset from the day after Visit 6 through the date of Visit 12. The Transition/Taper period will include all events with onset starting with the day after Visit 12 through Visit 15.

For Part 1, tables will present TEAE data by assigned treatment group received in Part 1. AEs occurring after enrollment and prior to the first administration of study treatment in Part 1 are defined as non-treatment emergent AEs (non-TEAEs).

AEs are categorized as related or unrelated. If the AE is thought to be definitely, probably or possibly related to study drug then it is to be categorized as related. Possibly or definitely unrelated is categorized as unrelated. Any TEAE with missing relationship will be considered as "related."

The severity of AEs (for both nonserious and serious AEs) will be assessed by the investigator as follows:

Severity Definition of Adverse Events:

Mild - A type of AE that is usually transient and may require only minimal treatment or therapeutic intervention. The event does not generally interfere with usual activities of daily living.

Moderate - A type of AE that is usually alleviated with additional specific therapeutic intervention. The event interferes with usual activities of daily living, causing discomfort but poses no significant or permanent risk of harm to the research participant.

Severe - A type of AE that interrupts usual activities of daily living, or significantly affects clinical status, or may require intensive therapeutic intervention.

Any AE with missing severity will be imputed as "severe."

The original terms used by the investigators in the eCRFs to identify AEs will be coded using the MedDRA Version 20.1 or later.

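### The adverse-event period rules in SAP 9.3 conflict with 6.7: Titration starts at Visit 6, Taper/Transition ends at Visit 15 for everyone, and cardiac AEs from Visit 14 have no assigned class

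*SAP*

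**What the plan says.** Section 6.7 (Visit Windows) sets the rules for by-period tabulations:

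- Titration: "The Titration Period begins on the first full day of treatment (Study Day 1) and extends through Visit 6". Maintenance then runs from the day after Visit 6 through Visit 12. T+M has its own definition, from Study Day 1 through Visit 12.
- Taper/Transition: from the day after Visit 12 "through Visit 13 (Taper) or Visit 15 (Transition to Part 2".
- The Double Blind Treatment Period entry gives Visit 15 as the safety end date without separating taper from transition. For early discontinuers it gives Visit 13, or Visit 12 if no taper takes place.

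Section 9.3 (Adverse Events) states the rules again for TEAEs:

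- On Titration it says "The Titration Period will include all events with onset from the date of the Visit 6", and names no closing date.
- Its Maintenance rule has the same start and end as the one in 6.7.
- On the last period it says "The Transition/Taper period will include all events with onset starting with the day after Visit 12 through Visit 15", with no separate end for subjects who taper off.
- A Part 1 TEAE must begin once dosing in Part 1 is under way. The only upper limit in the definition sentence is the clause "but not on or after the first dose of study treatment in Part 2".
- The opening paragraph of 9.3 ends Part 1 AE observation at Visit 13 or Visit 15.

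On the cardiac follow-up visit, footnote k to Table 4 says: "Only adverse events related to cardiac safety will be collected at this visit". Footnote c restricts that visit to subjects who leave Part 1 early or who complete it without entering Part 2.

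**The concern.** Sections 9.3.1 and 9.3.2 use these periods directly. The overview table and five summaries by system organ class and preferred term are each planned for the full Part 1 period, Titration, Maintenance, T+M and Taper/Transition. The sentence in 9.3 is therefore the working rule that places each event in a column.

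The days it leaves out are the days on which dose is raised: Table 1 puts the titration steps on Study Days 1-14. A Titration table programmed from 9.3 would miss the onset events it exists to show, and would carry Maintenance events instead.

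The other two points are smaller. An end at Visit 15 has no meaning for subjects who taper off. An unclassified cardiac AE from Visit 14 could be counted as a Part 1 TEAE by one programmer and left out by another. The cardiovascular SAP names valvular heart disease and pulmonary arterial hypertension as important potential risks to monitor, so the choice should not be left open.

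**Working it through.** The plan gives no figure to reproduce. The check sets the texts side by side and counts days on the nominal visit schedule.

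**Inputs (Table 5).** Visit 6 is Study Day 15, ±4 days. Visit 12 is Day 99, ±4 days. Visit 13 is Day 113, ±4 days. Visit 14 falls 3 to 24 months after the last dose.

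| Period | Section 6.7 | Section 9.3 | Agree? |
|---|---|---|---|
| Titration | Day 1 through Visit 6 | from Visit 6, no end | No |
| Maintenance | Visit 6 + 1 day through Visit 12 | the same | Yes |
| Taper/Transition | Visit 12 + 1 day through Visit 13 (taper) or Visit 15 (transition); but Visit 15 as general safety end date | Visit 12 + 1 day through Visit 15 | No |

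**Gap before Visit 6.** The days with no sub-period are the Visit 6 day minus 1. Nominal: 15 - 1 = 14. Earliest allowed visit: 11 - 1 = 10. Latest: 19 - 1 = 18. Of the 16-week safety period (16 × 7 = 112 days), the nominal gap is 14/112 = 12.5% of days. That is also the share of TEAEs only if onset is constant over time, which is an assumption; the share is larger if onset is concentrated early.

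**Overlap after Visit 6.** Titration has no end in 9.3, so every Maintenance day is also a Titration day: 99 - 16 + 1 = 84 nominal days (Days 16-99). If a programmer closed Titration where Maintenance opens, it would shrink to Day 15 alone. Days 1-14 are unassigned on either reading.

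**Which tables change.**

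- Full Part 1: no change, because the TEAE definition starts at first intake.
- T+M: no change if built on the 6.7 definition. If built by joining the 9.3 sub-periods, Days 1-14 drop out.
- Titration: wrong as specified. Section 9.3.1 gives it the whole Safety Population as denominator, which fits a start at first dose and not at Visit 6.

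**Taper end.** The opening of 9.3 and the Taper/Transition entry of 6.7 both allow for Visit 13 or Visit 15. The sub-period rule of 9.3 and the general safety end date in 6.7 give Visit 15 only. Each section disagrees with itself, so pointing 9.3 at 6.7 would not settle it.

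**Cardiac AE reported at Visit 14.** Take a subject who does not enter Part 2, with onset after Visit 13. Onset is after first intake: yes. Onset is on or after a first Part 2 dose: no, as there is none. The event meets the TEAE sentence. It is outside the Visit 13/15 observation period and outside Titration, Maintenance and Taper/Transition as defined in 6.7.

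**After correction.** Nominal Days 1-15 are Titration, Days 16-99 are Maintenance, and Day 100 to Visit 13 or 15 is Taper/Transition. The periods join with no gap and no overlap.

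**The case against.** The strongest reply is that the Titration sentence has simply lost some words. Taken literally it has no end and overlaps Maintenance, so it cannot be the intended rule. Section 6.7 is the declared windowing rule, the Safety Population denominator implies a start at first dose, and the overall counts do not move. This stands as far as intent goes, and it limits the damage to the by-period tables. It does not remove the error: 9.3 is the rule specific to AEs, and the later SAP addendum adds further T+M TEAE tables without correcting it.

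On taper, routine AE observation for these subjects stops at Visit 13 anyway, so a nominal Visit 15 limit should add few events. That is fair, and it makes this part mostly a matter of consistency.

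A reader might infer that the TEAE window has no end for everyone who skips Part 2. The SAP does not support that. The opening of 9.3 ends AE observation at Visit 13 or 15, 6.7 gives early discontinuers a safety end date, and Section 9 reports safety over the 16-week treatment period. What remains is a TEAE sentence that does not repeat the limit, together with the cardiac AEs of Visit 14.

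A reader might also try to size that remainder from the 20% dropout allowance in Section 4.2, or from the ratio of follow-up times. Neither works. The allowance is a planning figure for dropout before Maintenance, and early leavers may enter Part 2 with sponsor approval. Only cardiac AEs are collected at Visit 14, so a ratio of follow-up times says nothing about TEAEs in general. Nor does the SAP show that this group differs by arm. AE comparisons carry no p-values, and ECG and ECHO findings, including those at Visit 14, fall under the separate cardiovascular SAP. The valve and pulmonary-pressure assessment does not rest on these TEAE tables.

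**Conclusion.** The point holds as a contradiction in the AE period rules. The Titration sentence is wrong as written. Followed literally, it leaves 14 nominal days (10 to 18 with the visit window) in no sub-period and places 84 nominal days in two. The effect is confined to by-period AE tables, provided T+M is built on the 6.7 definition. The Visit 15 end date conflicts with the Visit 13/15 split and appears in both 9.3 and 6.7. The classification of Visit 14 cardiac AEs is open, but only for subjects not entering Part 2; the number of events concerned cannot be derived from the document. No efficacy result, significance level or sample size depends on any of this. The day counts assume nominal visit days; the 12.5% is a share of days and becomes a share of events only under constant onset.

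**What to change.** Change the wording in two sections and add one table:

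1. In 9.3, define Titration as first dose through the date of Visit 6. Leave the Maintenance rule as it is.
2. In 9.3, end Taper at Visit 13 (Visit 12 if no taper is conducted) and Transition at Visit 15. Make the same split in the Visit 15 safety end date of the Double Blind Treatment Period entry in 6.7.
3. In the TEAE definition, add that for subjects not entering Part 2 the Part 1 window closes at those same dates.
4. State that cardiac AEs collected at Visit 14 are post-treatment events, tabulated separately by arm.

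The cost is a short SAP amendment or addendum entry, a check that the by-period AE programs follow the corrected rule, and one additional table. No new data are needed, and nothing in dosing or clinical management changes.

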9.3.1. Overview of Adverse Events

The number and percent of subjects with at least one of the following events will be summarized in an overall summary table:

- TEAE
- Related TEAE
- Serious TEAE

- Related serious TEAE
- Severe TEAEs
- Severe related TEAE
- Adverse events of special interest
- TEAEs leading to premature discontinuation of study treatment
- TEAEs leading to premature discontinuation from the study
- Death

authorization areof. This overall summary table will be presented for the full Part 1 period, Titration Period Maintenance Period, Titration + Maintenance Period, and Taper/Transition Period.

For the full Part 1 period, Titration Period, and Titration + Maintenance Period, the denominator for the calculation of percentage will be the number of subjects in the SAF for the treatment group. For the Maintenance Period, the denominator for the calculation of the percentage will be the number of subjects for the treatment group with Part 1 last dose strictly greater than the date of Visit 6. For the Taper/Transition Period, the denominator for the calculation of the percentage will be the number of subjects for the treatment group with last dose strictly greater than the date of Visit 12.

9.3.2. **Treatment Emergent Adverse Events**

The following summaries will display the number and percentage of subjects with an adverse event as well as the corresponding number of events by system organ class (SOC) and preferred term (sorted alphabetically):

- All TEAEs
- Serious TEAEs
- TEAEs by Maximum Severity
- Study Drug Related TEAEs
- All TEAEs leading to premature discontinuation from the study

These summaries will present the TEAEs presented for the full Part 1 period, Titration Period, Maintenance Period, Titration + Maintenance Period, and Taper/Transition Period.

Summaries of TEAEs and Study Drug Related TEAEs will be summarized for the following subgroups:

- Age: 2- <6 years, 6-<12 years, 12 <18, $\ge 18 35$ years.
- Sex

- Concomitant usage of most commonly used concomitant Anti-epileptic medications (e.g. Valproate or other medications of interest; to be determined)
- # of con AEDs

One additional summary table will summarize the number and percent of subjects in each treatment group who experience an AE that occurs in at least 5% of subjects in any treatment group. For AEs occurring in at least 5% of subjects, the mean and median time to onset and the median duration of the onset will be presented. The summary will be presented by preferred term in decreasing order of incidence.

No inferential statistical methods (i.e., methods that yield p-values) will be used to compare treatment groups on the frequency or severity of AEs.

The following listings will be produced for all enrolled subjects:

- All AEs, events considered to be TEAE will be identified in the listing
- Serious AEs
- · AEs that lead to premature discontinuation from the study
- Deaths

9.3.3. Adverse Events of Special Interest (AESI)

As per International Conference on Harmonisation (ICH) guidance (E2F Development Safety Update Report [2011]), the sponsor has identified the following AESIs for the ZX008 in the table below-

Table 7 - Adverse Events of Special Interest:

Metabolic/Endocrine
1.Elevated prolactin level ≥2x above the upper limit of normal (ULN)
2. Hypoglycemia - <3.0 mmol/l or 54 mg/dl, whether that level is associated with
symptoms or not
X Y , O
Neuropsychiatric
1. Suicidal thoughts, ideation or gestures

Standardized MedDRA Queries (SMQs) will be employed as applicable to identify each AESI category or manually assigned through review. For Part 1 AEs, this will be completed and documented prior to study unblinding.

For Part 1, adverse events of special interest will be summarized by treatment group and by system organ class and preferred term.

All AESIs will be listed separately.

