9.1. EXTENT OF EXPOSURE

Part 1 treatment exposure data will be summed.

Duration of total exposure.

Duration of total exposure during Part 1 (i.e., time on treatment (in days)) will be calculated per subject as the number of days with IMP intake during the trial and will be summarized using n, mean, standard error, median, minimum, Q_1 , Q_3 and maximum.

This will be calculated for non-placebo subjects as:

Date of last IMP intake in Part 1 - Date of first full daily IMP intake in Part 1 + 1 Time on treatment will be summarized by the Part 1 treatment group.

TREATMENT COMPLIANCE (DIARY) 9.2.

Study medication is to be administered twice daily, and self-reported compliance is recorded in the eDiary as full (both doses), partial (less than full daily dose) or missed (both doses) each day. From this, compliance will be calculated by assuming that a missed dose=0% of dose consumed, partial=50% of dose consumed, and full=100% of dose consumed. For each subject, a daily diary compliance score will be thus obtained.

A compliance will also be determined based on the actual quantity taken, determined using the weight of the dispensed drug kit and weight of the returned drug kit. The expected quantity taken will be determined using the assigned dosage in mg/kg/day and the number of days they were assigned at that dosage. If a kit was not returned, the compliance for the period will be missing.

For Part 1, compliance will be summarized for the SAF and mITT populations over the course of T+M period and M period only per recorded visit dates, reported by treatment group.

9.3. **ADVERSE EVENTS**

An AE is defined as any unfavorable and unintended sign (including an abnormal, clinically significant laboratory finding), symptom, or disease temporally associated with the use of a medicinal (investigational) product, whether or not considered related to the medicinal (investigational) product. For Part 1, the period of observation for adverse events extends from the time the subject gives informed consent until the end of the titration/transition period (Visit 13 or 15).

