Listings of the most extreme values for a subject recorded in Part 1 and Part 2 will be created for each parameter. These will show the lowest recorded value and the highest recorded value noted for the subject. A listing of subjects with markedly abnormal laboratory results will be provided, and additional explorations of the data may be conducted as warranted.

Additionally, summaries of abnormal lab results by parameter will be provided to investigate changes in platelet count and prolactin in detail. The summaries include:

- Subjects with decrease (≥25% from baseline) in Platelets count with normal platelet count at baseline
- Subjects with decrease (≥25% from baseline) in Platelets count relative to baseline (whether normal or abnormal) platelet count
- Subjects with decrease (≥25% from baseline) in Platelets count with normal platelet count at baseline, by valproate use
- Subjects with decrease (≥25% from baseline) in Platelets count with normal platelet count at baseline, by presence/absence of infection event prior to 7 days of the lab assessment
- Subjects with increase (≥25% from baseline) in prolactin with normal baseline
- Subjects with increase (≥25% from baseline) in prolactin with normal baseline, and had seizure event within 48 hours prior to prolactin

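### Two events of special interest are defined by laboratory thresholds, but they are identified from adverse-event records and no planned table counts either threshold by arm

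*SAP*

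**What the plan says.** **Definition.** Table 7 in SAP section 9.3.3 lists three AESIs, two of which are laboratory levels. One is "Elevated prolactin level ≥2x above the upper limit of normal (ULN"), read here as at least twice the ULN. The other is "Hypoglycemia - <3.0 mmol/l or 54 mg/dl, whether that level is associated with" symptoms or not. Neither definition has a condition on baseline or on clinical significance.

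**Identification.** The rule is "Standardized MedDRA Queries (SMQs) will be employed as applicable to identify each AESI category or manually assigned through review". The next sentence shows which records it works on: "For Part 1 AEs, this will be completed and documented prior to study unblinding".

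**Tabulation.** In Part 1, "adverse events of special interest will be summarized by treatment group and by system organ class and preferred term". In the index these are Tables 14.3.1.8 and 14.3.1.9.

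**When a laboratory value is an AE.** Section 9.3 defines an AE as "any unfavorable and unintended sign (including an abnormal, clinically significant laboratory finding").

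**Laboratory outputs.** Section 9.10 plans:
- shift tables with five levels: within limits, and below or above limits with or without clinical significance;
- listings of each subject's lowest and highest value;
- a listing of markedly abnormal results, for which it gives no criterion;
- prolactin summaries that begin with "Subjects with increase (≥25% from baseline) in prolactin with normal baseline", followed by the same group restricted to those with a recent seizure.

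The output index in the SAP addendum keeps the same prolactin tables.

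**The concern.** A threshold-defined event should be counted from the measurements that define it. The central laboratory measures both glucose and prolactin, yet the SAP has no step that derives either AESI from those results. The AESI count by arm therefore depends on which values were entered as adverse events and under what term.

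The sponsor itself named these risks, and the AESI tables are where a reader will look for their frequency by arm. If those counts do not match Table 7, the reader needs a laboratory table at the same cut-offs, and none is planned. The only dedicated prolactin table uses a different cut-off and a restricted population.

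**Working it through.** The SAP gives no figure to reproduce here. The check sets the rules side by side and compares the two prolactin criteria.

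**1. Does AE-based identification reproduce Table 7?** Table 7 needs a value. An SMQ or a preferred term supplies a name without a value. Two kinds of mismatch follow:
- A glucose of 2.8 mmol/l, or a prolactin of 2.5x ULN, that was not reported as an AE meets Table 7. No stated SAP rule brings it into Tables 14.3.1.8 or 14.3.1.9.
- A reported hypoglycaemia at 3.4 mmol/l, or a reported prolactin increase at 1.5x ULN, does not meet Table 7. A term search could still pick it up.

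The two glucose units agree: with an assumed conversion factor of 18.016, 3.0 × 18.016 = 54.05 mg/dl.

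**2. Does the 25% prolactin table stand in for the AESI?** Let b be baseline and p the post-baseline value, both in multiples of ULN.
- AESI rule (Table 7): p ≥ 2, any b.
- Prolactin table rule (section 9.10): b ≤ 1 and p ≥ 1.25b.

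*Normal baseline.* If b ≤ 1 and p ≥ 2, then p/b ≥ 2, which exceeds 1.25. Every normal-baseline subject who reaches the AESI level is in the table. A grid of b from 0.01 to 1.00 against p from 2.00 to 5.99 agreed, with 0 cases missed.

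*Separation.* The rise needed to reach 2x ULN is (2/b − 1) × 100%, against 25% for entry to the table.

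| Baseline (x ULN) | Value that enters the table (x ULN) | Rise needed to reach 2x ULN |
|---|---|---|
| 0.4 | 0.50 (still normal) | 400% |
| 0.8 | 1.00 (still normal) | 150% |
| 1.0 | 1.25 | 100% |
| 1.2 | not eligible | 66.7% |
| 1.7 | not eligible | 17.6% |

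A change from 0.50 to 0.63 (0.63/0.50 = 1.26, +26%, still normal) counts the same as one from 0.9 to 2.1 (2.1/0.9 = 2.33, +133%, above the AESI level).

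*Raised baseline.* A subject going from 1.2 to 3.0 (3.0/1.2 = 2.5, +150%) meets Table 7 and is not in the table, because b > 1.

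**3. Do the other laboratory outputs count the thresholds?**
- Shift tables: 2x ULN falls inside the above-limit levels and 3.0 mmol/l has no level of its own, so neither can be read off.
- Extreme-value listings: section 9.10 promises them for each parameter. The SAP index names them for hematology, biochemistry (which includes glucose) and urinalysis, with none for the growth and puberty group that contains prolactin. A listing also gives no count by arm.
- Markedly abnormal listing: with no criterion, it cannot be matched to Table 7.

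**4. What the SAP does elsewhere.** For platelets, section 9.10 plans a normal-baseline count and also one whatever the baseline. For weight and BMI, section 9.6 counts subjects crossing 7% and 10% directly from the measurements. For the third AESI, suicidality, section 9.11 gives an instrument-based count by arm from the C-SSRS. Only the two laboratory AESIs have no measurement-based count.

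**The case against.** The strongest case against has four parts.

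**The review route.** Section 9.3.3 allows manual assignment through review as well as SMQs, and that review might include laboratory results. This stands as a possibility. However, the SAP does not say what is reviewed, and a step described for Part 1 AEs with output by preferred term points to AE records.

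**Reporting rules.** AESIs have their own row in the schedule of assessments (Table 4), and the protocol, which is not shown, may require every threshold value to be reported. This also stands. It rules out saying that silent cases never reach the AESI tables. A reader might also take section 9.3 to admit only clinically significant laboratory values. Its wording is inclusive, "including an abnormal, clinically significant laboratory finding", and Table 7 counts hypoglycaemia without symptoms.

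**Purpose of the 25% table.** Section 9.10 offers it as an additional, detailed look at prolactin changes and does not call it the AESI analysis. That is fair: two cut-offs for two purposes do not contradict each other. It leaves open that nothing else counts the AESI level.

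**Visibility.** Shift tables and listings keep individual cases partly visible, and AE summaries carry no p-values under section 9.3.2. Both points are true and limit the weight of the concern. Finding cases by hand in listings is still no pre-specified count by arm.

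**Conclusion.** The point holds in this form: the SAP defines two AESIs by laboratory thresholds, gives no laboratory-based derivation of either, and plans no by-arm count at either threshold. The prolactin table neither isolates the AESI nor fully covers it.

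Two stronger readings are tempting and are not supported. One is that the AESI tables can only undercount. Terms carry no value, so error can go either way, and its direction depends on reporting rules not shown here. The other is that the prolactin table misses the named risk. It includes every normal-baseline subject who reaches 2x ULN. What it lacks is separation from small rises, and subjects with a raised baseline.

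The size cannot be stated in subjects: the documents do not say how many had raised baseline prolactin, crossed a threshold, or had a threshold value that went unreported. The examples above show how the rules behave and do not estimate frequency. The conclusion assumes that the manual review works on AE records, as the text suggests. If it already screens central-laboratory values against Table 7, the remaining gap is that the SAP does not say so and does not tabulate the result. This is a cheap improvement to a descriptive safety summary and does not bear on the efficacy conclusions.

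**What to change.** Add to section 9.3.3 or 9.10, and to the index, one table by treatment arm on the Safety Population from the central-laboratory data, including unscheduled samples. It should give the number and percentage of subjects with any post-baseline prolactin at least 2x ULN and, separately, any post-baseline glucose below 3.0 mmol/l, whatever the baseline. Beside each count, show how many of those subjects also had the AESI reported as an AE, and how many reported AESIs had no laboratory value beyond the threshold. State what the manual review examines. Keep the 25% prolactin table as supportive.

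The cost is a few lines of SAP text and one extra table from data already collected. The reported AESI frequency may become less favourable.
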